6.3. Lifestyle and/or Dietary Requirements

Throughout the study, subjects may undergo medical assessments and review of compliance with requirements before continuing in the study.

6.3.1. Meals and Dietary Restrictions

Subjects should fast overnight for at least 8 hours before dosing (water permitted).

6.3.2. Caffeine, Alcohol, and Tobacco

Subjects should not be allowed caffeine consumption for 12 hours prior to CRU admission and when in the CRU. At other times during the outpatient period, subjects will be allowed to maintain their regular caffeine consumption.

Alcohol consumption is not allowed from 12 hours prior to all study visits and during CRU stays. At all other times, alcohol consumption should be limited to 2 units per day (1 unit alcohol equals 1/2 pint [285 mL] of beer, 1 glass [125 mL] of wine or 25 mL of distilled spirits).

Subjects who smoke should maintain a stable smoking habit throughout the study. Subjects will be asked to refrain from smoking for approximately 1 hour prior to each ECG and vital sign measurements as well as abide by the CRU smoking guidelines.

6.3.3. Poppy Seeds

Foods and beverages containing poppy seeds will not be allowed from 7 days prior to screening until final discharge from the study.

6.3.4. Activity

Subjects will be advised to maintain their regular levels of physical activity/exercise during the study, but refrain from vigorous exercise. Strenuous activity should be avoided from 24 hours prior to admission until discharge from the CRU. When certain study procedures are in progress at the site, subjects may be required to remain recumbent or sitting.

6.4. Screen Failures

Subjects who do not meet the criteria for participation in this study (screen failure) may not be rescreened.

7. Treatment

7.1. Treatment Administered

The proposed LY3074828 test formulation will be prepared extemporaneously as sterile solutions for SC injection and IV infusion, as described in the pharmacy instructions provided by the sponsor to the site. The clinical material for extemporaneous preparation will be supplied as a frozen solution by Lilly.

The LY3074828 reference formulation previously used in Phase 1 and 2 studies will be supplied to the site by Lilly as a sterile lyophilized vial to be reconstituted prior to injection as detailed in the pharmacy instructions.

- The actual date and time of all dose preparation and administration will be documented and drug accountability records will be maintained by the site pharmacy.

Table AMAL.3 shows the treatment regimens.

Injection sites selected for SC administration should be the abdominal region approximately 5 cm from the umbilicus and the treatment administered with the needle applied at approximately 45 degrees with pinching of the skin. Subcutaneous administration of LY3074828 should be given by a limited number of individuals for consistency. The same type of syringe and needle (27-gauge, half-inch needle) should be used for all subjects to ensure all injections are delivered to a consistent depth target into the SC space. Where 2 or more injections are to be administered, the subsequent injection(s) should be given immediately following the previous and administered to another abdominal quadrant. Further information around SC administration will be in pharmacy handling instructions.

The IV formulation of LY3074828 will be administered as a slow IV infusion over at least 30 minutes. The site must have resuscitation equipment, emergency drugs, and appropriately trained staff available during and for at least 6 hours after subjects complete their treatment administration. Further information around IV administration will be in pharmacy handling instructions.

Investigational product will be prepared at the site by unblinded pharmacists or other trained personnel. Investigational product will only be administered to subjects on-site by nurses or other trained personnel.

Table AMAL.3. Treatments Administered

| LY3074828 | | | | |
|---------------------------------------|--|------------------------------|-------------------------------|----------------------------|
| Treatment | Reference (N = 18) | Test SC 2 × 1-mL (N = 18) | Test SC 1 × 2-mL (N = 18) | Test IV (N = 18) |
| Regimen | 250 mg SC ^a | 250 mg SC | 250 mg SC | 250 mg IV |
| Drug Product formulation | reference | test | test | test |
| LY3074828 concentration | 72 mg/mL | 125 mg/mL | 125 mg/mL | 250 mg/10 mL (25 mg/mL) |
| Volume per dose | 2 × 1 mL + 1 × 1.5 mL (3.5 mL total) | 2 × 1 mL (2 mL total) | 1 × 2 mL (2 mL total) | 10 mL infusion |
| Infusion or injection duration | NA | NA | Slow versus fast ^b | ≥30 minutes |

Abbreviations: IV = intravenous; NA = not applicable; SC = subcutaneous.

a Theoretical total dose 252 mg for Reference.

b Odd number subjects will be injected slowly, approximately over 15 seconds and even number subjects will receive the injection over 5 to 10 seconds.

The investigator or designee is responsible for:

- explaining the correct use of the investigational product(s) to the site personnel,
- verifying that instructions are followed properly,
- maintaining accurate records of investigational product dispensing and collection,
- and returning all unused medication to Lilly or its designee at the end of the study.

Note: In some cases, sites may destroy the material if, during the investigative site selection, the evaluator has verified and documented that the site has appropriate facilities and written procedures to dispose of clinical trial materials.

7.1.1. Packaging and Labeling

LY3074828 will be supplied to the investigator by Lilly. Clinical trial materials are manufactured in accordance with good manufacturing practices. All investigational products will be stored, inventoried, reconciled, and destroyed according to applicable regulations.

LY3074828 reference formulation will be supplied for clinical trial use as sterile, lyophilized powder in a glass vial and should be stored under refrigerated conditions (2°C to 8°C). Each vial is manufactured to deliver 75 mg of LY3074828 and will be reconstituted with sterile water to a concentration of 72 mg/mL. Contents from multiple vials will be pooled for each injection, as required.

LY3074828 test formulation will be supplied as a frozen solution at a concentration of 125 mg/mL, with approved excipients added. The solution will be thawed at the site, pooled, and undergo terminal sterile filtration into sterile vials before being prepared for clinical trial use, in accordance to the pharmacy instructions provided by the sponsor. The content of the extemporaneously prepared sterile vials will either be dispensed into syringes for SC administration or further diluted for IV administration to the trial subjects.

Clinical trial materials will be labeled according to the country's regulatory requirements.

7.2. Method of Treatment Assignment

Subjects will be randomized to 1 of 4 treatments using a computer-generated allocation schedule.

7.2.1. *Timing of Doses*

The actual time of all dose administrations will be recorded in the subject's electronic case report form (eCRF).

7.3. Blinding

This is an open-label study.

7.4. Dose Modification

Dose adjustments are not permitted in this study.

7.4.1. *Special Treatment Considerations*

7.4.1.1. *Premedication for Infusions*

Premedication for the subjects randomized to receive LY3074828 as an IV infusion is not planned. However, if an infusion reaction occurs, appropriate medication may be used as determined by the study investigator(s) and documented in the eCRF. If one Grade 2 infusion reaction is observed, paracetamol/acetaminophen, 500 to 1000 mg and/or an antihistamine (such as diphenhydramine) will be administered orally 30 to 60 minutes prior to the start of infusion for all subsequent subjects.

The decision to implement premedication for infusions in subsequent subjects will be made by the investigator and recorded in the study eCRF as a concomitant therapy for prophylaxis purpose (see Section 7.7).

7.4.1.2. *Management of Infusion Reactions*

Due to the risk of an infusion reaction with any biological agent, all subjects should be monitored closely. Symptoms and signs that may occur as part of an infusion reaction include, but are not limited to, fever, chills, nausea, headache, bronchospasm, hypotension, angioedema, throat irritation, rash, pruritus, myalgia, and dizziness. In the event that a significant infusion reaction occurs, the following guidance should be followed:

- the investigational product infusion should be slowed or stopped, depending on the symptoms/signs present

- if slowed, the infusion should be completed at the slower rate, as tolerated
- if stopped, one attempt to restart at half the original rate will be allowed
- supportive care should be employed in accordance with the symptoms/signs

7.4.1.3. Safety Protocol in the Event of a Retrospective Positive Sterility Finding from extemporaneously prepared study treatment

If a positive sterility finding were to arise in the terminally sterile filtered product, the subjects who were dosed from the impacted batch should be immediately contacted and asked to return to the CRU for a full medical examination. This should include a physical examination, including blood pressure, pulse rate and body temperature. Blood samples should be collected for culture and assayed for inflammatory markers such as C-Reactive Protein and elevations in white blood cell counts.

If the signs and symptoms indicated a subject is suffering from possible infection(s), they will be clinically managed, treated and followed up until resolution. Any adverse events will be recorded as appropriate.

7.5. Preparation/Handling/Storage/Accountability

Only participants enrolled in the study may receive investigational product and only authorized site staff may supply or administer study treatment. All study treatments should be stored in an environmentally controlled and monitored (manual or automated) area in accordance with the labeled storage conditions (see Section 7.1.1) with access limited to the investigator and authorized site staff.

The investigator, institution, or the head of the medical institution (where applicable) is responsible for study treatment accountability, reconciliation, and record maintenance (such as receipt, reconciliation, and final disposition records).

7.6. Treatment Compliance

The investigational product will be administered at the clinical site, and documentation of treatment administration will occur at the site.

7.7. Concomitant Therapy

Over-the-counter or prescription medication, including herbal medications such as St. John's Wort, are not permitted within 14 days prior to dosing and throughout the study. However, stable doses of oral contraceptive or hormone replacement therapy may be allowed as per judgment of the investigator. Paracetamol/acetaminophen (up to 2 g/day) may be allowed at the investigator's discretion. Any other drugs are to be avoided during the study unless required to treat an AE. If the need for concomitant medication arises, inclusion or continuation of the subject may be at the discretion of the investigator after consultation with a Lilly clinical pharmacologist or clinical research physician. Any additional medication used during the course of the study must be documented.

7.8. Treatment after the End of the Study

Not applicable for this study.

8. Discontinuation Criteria

8.1. Discontinuation from Study Treatment

The reason for and date of discontinuation will be collected for all subjects. All randomized subjects who discontinue after receiving study drug will have ED procedures performed as shown in the Schedule of Activities (Section 2).

8.1.1. Discontinuation of Inadvertently Enrolled Subjects

If the Sponsor or investigator identifies a subject who did not meet enrollment criteria and was inadvertently enrolled, the subject will be discontinued from the study and ED assessments will be performed as described in the Schedule of Activities (Section 2).

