- b Required for subjects receiving IV treatments only.
- c All female subjects of childbearing potential will have serum pregnancy test at screening. For women who are considered to be postmenopausal, follicle-stimulating hormone should be drawn to confirm postmenopausal status as defined in inclusion criterion [1b]; women with confirmed postmenopausal status can be exempted from further pregnancy tests during the study.
- d Within 7 to 14 days after the last procedure or upon ED.
- e Required for subjects receiving SC treatments only – time allowance of ±5 minutes.

3. Introduction

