- Pharmacokinetic results from Study AMAA indicate that serum exposure of LY3074828 increases in a dose-proportional manner. The mean half-life associated with the terminal rate constant ($t_{1/2}$) was 10.5 days and did not appear to be dependent on dose. The overall mean clearance following IV administration was approximately 0.526 L/day and is within the range expected for human monoclonal antibodies. Maximum concentrations were observed 3 days postdose following SC administration. Based on the area under the concentration versus time curve (AUC), the SC bioavailability was 40%.

- Treatment-emergent anti-drug antibodies (TE-ADAs) developed in 3 subjects after administration of single IV doses of LY3074828, (120 mg, 2 subjects; 350 mg, 1 subject). No subject had TE-ADAs after SC administration. There was no correlation between TE-ADA titers and the doses of LY3074828.

The clinical phase of Study I6T-MC-AMAD (AMAD) has been completed. A total of 43 healthy Japanese and Caucasian subjects were administered LY3074828 or placebo via either IV infusion (60 to 1200 mg) or SC injection (200 mg) in a Phase 1, single-site, subject- and investigator-blind, randomized, placebo-controlled, single-dose study. Subjects were followed-up for up to 12 weeks following the single dose of study drug.

- No SAEs and no AEs considered related to study drug were reported. The reported TEAEs were not dose dependent. There were no infusion reactions or injection site reactions. There were no clinically significant findings in vital signs, ECGs, or clinical laboratory tests, except for 1 subject having an abnormal ECG finding that was mild and not considered to be related to study drug.
- Preliminary PK data available from Study AMAD indicate that the PK of LY3074828 are similar in Japanese and Caucasian subjects.

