5.1. Overall Design

Study AMAL is a single-center, randomized, parallel-treatment, open-label, Phase 1 single-dose administration study evaluating LY3074828 in 72 healthy subjects.

Screening Period (≤ 4 weeks): Subjects will be evaluated for study eligibility ≤ 28 days prior to enrollment.

Residential Period (2 days): Subjects who fulfill the eligibility criteria will be randomized to 1 of 4 treatments, with 18 subjects randomized to each treatment, as shown below:

- **Reference:** 250 mg LY3074828; lyophilized reference formulation with $2 \times 1\text{-mL} + 1 \times 1.5\text{-mL}$ SC injections;
- **Test SC $2 \times 1\text{-mL}$:** 250 mg LY3074828; test formulation with $2 \times 1\text{-mL}$ SC injections;
- **Test SC $1 \times 2\text{-mL}$:** 250 mg LY3074828; test formulation with $1 \times 2\text{-mL}$ SC injection;
- **Test IV:** 250 mg LY3074828; test formulation by IV infusion over at least 30 minutes.

Subjects will report to the clinical research unit (CRU) on Day -1 and remain at the CRU until after the scheduled procedures have been completed on Day 2 as defined in the Schedule of Activities (Section 2). After randomization, study drug will be administered by either IV infusion or SC injection in the morning of Day 1 after an overnight fast. Subjects within the same enrollment group may be dosed across several days if required by the site for logistical or other purposes.

Outpatient Follow-up Period (approximately 14 weeks): The follow-up period will include outpatient visits for a total of 12 weeks following Day 1 dose administration to assess tolerability and PK of LY3074828. An end-of-study follow-up visit will be scheduled within 7 to 14 days after the last procedure or upon early discontinuation (ED).

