- [23] have used or intend to use over-the-counter or prescription medication, including herbal medications such as St. John's Wort within 14 days prior to dosing (stable doses of oral contraceptive or hormone replacement therapy may be allowed as per judgment of the investigator)
- [24] have donated blood of more than 500 mL within the last month prior to screening
- [25] have an average weekly alcohol intake that exceeds 28 units per week (males) and 21 units per week (females), (1 unit alcohol equals 1/2 pint [285 mL] of beer, 1 glass [125 mL] of wine, or 25 mL of distilled spirits) and/or show positive findings on ethanol testing and/or who are unwilling to abide by the alcohol restrictions described in Section [6.3.2](#)
- [26] are subjects whose tobacco consumption is more than 10 cigarettes per day or the equivalent or subjects who are not willing to refrain from smoking for approximately 1 hour prior to each ECG and vital sign measurement during the study or who are unwilling to abide by the CRU smoking guidelines described in Section [6.3.2](#)
- [27] have had symptomatic herpes zoster within 3 months of screening
- [28] show evidence of active or latent tuberculosis (TB), as documented by medical history and examination and TB testing: a negative (not indeterminate) QuantiFERON®-TB Gold test, or have had household contact with a person with active TB, unless appropriate and documented prophylaxis for TB has been given.
- [29] have received live vaccine(s) (including attenuated live vaccines, and those administered intranasally) within 1 month of screening, or intend to during the study
- [30] are immunocompromised
- [31] have received treatment with biologic agents (such as monoclonal antibodies, including marketed drugs) within 3 months or 5 half-lives (whichever is longer) prior to dosing.
- [32] have significant allergies to humanized monoclonal antibodies
- [33] have clinically significant multiple or severe drug allergies, or intolerance to topical corticosteroids, or severe post treatment hypersensitivity reactions (including, but not limited to, erythema multiforme major, linear immunoglobulin A dermatosis, toxic epidermal necrolysis, or exfoliative dermatitis)
- [34] have had lymphoma, leukemia, or any malignancy within the past 5 years except for basal cell or squamous epithelial carcinomas of the skin that have been resected with no evidence of metastatic disease for 3 years
- [35] have had breast cancer within the past 10 years

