9.2.1. Serious Adverse Events

An SAE is any AE from this study that results in one of the following:

- death
- initial or prolonged inpatient hospitalization
- a life-threatening experience (that is, immediate risk of dying)
- persistent or significant disability/incapacity
- congenital anomaly/birth defect
- important medical events that may not be immediately life-threatening or result in death or hospitalization but may jeopardize the patient or may require intervention to prevent one of the other outcomes listed in the definition above. Examples of such medical events include allergic bronchospasm requiring intensive treatment in an emergency room or at home, blood dyscrasias or convulsions that do not result in inpatient hospitalization, or the development of drug dependency or drug abuse.

Study site personnel must alert Lilly, or its designee, of any SAE within 24 hours of investigator awareness of the event via a sponsor-approved method. If alerts are issued via telephone, they are to be immediately followed with official notification on study-specific SAE forms. This 24-hour notification requirement refers to the initial SAE information and all follow-up SAE information.

Although all AEs are recorded in the eCRF after signing informed consent, SAE reporting begins after the subject has signed informed consent and has received investigational product. However, if an SAE occurs after signing informed consent, but prior to receiving investigational product, AND is considered reasonably possibly related to a study procedure then it MUST be reported.

Investigators are not obligated to actively seek AEs or SAEs in subjects once they have discontinued from and/or completed the study (the subject summary eCRF has been completed). However, if the investigator learns of any SAE, including a death, at any time after a subject has

been discharged from the study, and he/she considers the event reasonably possibly related to the study treatment or study participation, the investigator must promptly notify Lilly.

Pregnancy (maternal or paternal exposure to investigational product) does not meet the definition of an AE. However, to fulfill regulatory requirements any pregnancy should be reported following the SAE process to collect data on the outcome for both mother and fetus.

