9.4.7. Immunogenicity Assessments

Blood samples for immunogenicity testing will be collected to determine antibody production against the investigational product as specified in the Schedule of Activities (Section 2).

A risk-based approach will be used to monitor subjects who develop TE-ADAs during and following treatment with LY3074828. TE-ADAs are defined as either 2-fold increase in titer (i.e. 1:20) above the minimum required dilution (1:10) if no ADAs were detected at baseline or a 4-fold or greater increase in titer over baseline for subjects that are ADA positive at baseline. LY3074828 is a monoclonal antibody that binds to p19 of IL-23, and there is no unique/non-redundant endogenous protein counterpart, greatly minimizing the risk of cross-reactive ADA. Any potential risks of ADA development following this single dose trial would be dependent on LY3074828 exposure outside of this clinical trial. The largest potential risk would be reaction upon subsequent drug exposure that could range in severity from mild local injection site reactions to systemic anaphylaxis and/or systemic immune complex disease (Arthus-reaction). These potential risks would likely be associated with higher serum concentrations of ADA.

Given that the subjects have only a single exposure to LY3074828, any ADA response is anticipated to peak and then diminish due to lack of additional exposures. Subjects will have ADA sampling at baseline, Day 15, Day 29, Day 85, and at follow-up. Subjects that are observed to have significant (i.e. greater than 1:1000 titer) and non-decreasing titers that meet the definition of TE-ADA, will be requested to return every 3 months after the last sample to have follow-up ADA samples tested until the titer has returned to within 1 titer of their baseline or is clearly trending back to the baseline titer. The rationale for the definitions of both TE-ADA and return to baseline is based on the premise that a 1-titer change may result from expected assay variability.

Subjects followed for at least 1 year since last dose who have not returned to baseline, as defined above, will be assessed for safety concerns and, if no clinical sequelae are recognized by the clinical team, no further follow-up will be required. Subjects who have clinical sequelae that are considered potentially related to the presence of TE-ADA may also be asked to return for additional follow-up testing.

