Appendix 1. Abbreviations and Definitions

| Term | Definition |
|--------------------------------|--|
| ADA | anti-drug antibody |
| AE | adverse event: Any untoward medical occurrence in a patient or clinical investigation subject administered a pharmaceutical product that does not necessarily have a causal relationship with this treatment. An AE can therefore be any unfavorable and unintended sign (including an abnormal laboratory finding), symptom, or disease temporally associated with the use of a medicinal (investigational) product, whether or not related to the medicinal (investigational) product. |
| AUC | area under the concentration versus time curve |
| AUC(0-∞) | area under the concentration versus time curve from time zero to infinity |
| AUC(0-t_{last}) | area under the concentration versus time curve from time zero to time t, where t is the last sample with a measurable concentration |
| BMI | body mass index |
| CD | Crohn's disease |
| CI | confidence interval |
| CL/F | apparent total body clearance of drug calculated after extra-vascular administration |
| C_{max} | maximum observed drug concentration |
| complaint | A complaint is any written, electronic, or oral communication that alleges deficiencies related to the identity, quality, purity, durability, reliability, safety or effectiveness, or performance of a drug or drug delivery system. |
| compliance | Adherence to all the trial-related requirements, good clinical practice (GCP) requirements, and the applicable regulatory requirements. |
| confirmation | A process used to confirm that laboratory test results meet the quality requirements defined by the laboratory generating the data and that Lilly is confident that results are accurate. Confirmation will either occur immediately after initial testing or will require that samples be held to be retested at some defined time point, depending on the steps required to obtain confirmed results. |
| CRU | clinical research unit |
| EC | Ethics Committee |
| ECG | electrocardiogram |
| eCRF | electronic case report form |
| ED | early discontinuation |
| enroll | The act of assigning a subject to a treatment. Subjects who are enrolled in the trial are those who have been assigned to a treatment. |

| | |
|-------------------------|--|
| enter | Subjects entered into a trial are those who sign the informed consent form directly or through their legally acceptable representatives. |
| GCP | good clinical practice |

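### Section 8.1.1 takes an ineligible subject out of the study even after the single dose, replacing the remaining safety, ADA and PK visits with one early-discontinuation visit

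*Protocol*

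**What the plan says.** Protocol 8.1.1 is mandatory. Once the sponsor or investigator finds that a subject did not meet the entry criteria, "the subject will be discontinued from the study and ED assessments will be performed as described in the Schedule of Activities". It does not separate undosed from dosed subjects and leaves no discretion.

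Two other places show that it reaches dosed subjects. Appendix 1 defines enrollment by allocation: "Subjects who are enrolled in the trial are those who have been assigned to a treatment". Protocol 8.1 attaches the ED procedures to randomized subjects who leave after receiving drug, and these are the procedures that 8.1.1 calls for.

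The Schedule of Activities has one combined follow-up/ED column, timed in footnote d as "Within 7 to 14 days after the last procedure or upon ED". An ED visit therefore takes the place of the end-of-study visit. On what follows, Protocol 9.2.1 says: "Investigators are not obligated to actively seek AEs or SAEs in subjects once they have discontinued from and/or completed the study".

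The follow-up given up is 12 weeks of outpatient visits after the Day 1 dose (Protocol 5.1). For immunogenicity, Protocol 9.4.7 states: "Subjects will have ADA sampling at baseline, Day 15, Day 29, Day 85, and at follow-up".

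**The concern.** Discontinuing an ineligible subject before dosing is sensible, because it prevents an exposure that should not happen. After the only dose has been given, exposure cannot be reduced. What changes is how closely the subject is watched: scheduled adverse event reviews, laboratory tests, ADA samples, PK samples and, for women of childbearing potential, pregnancy tests all stop after the ED visit.

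This can happen while much of the antibody is still present. Protocol 3.2 reports that the mean half-life "was 10.5 days and did not appear to be dependent on dose", and exclusion criterion 31 counts five half-lives (or 3 months, if longer) as the washout for earlier biologics. A subject removed in the first weeks would be released from active follow-up well inside that period. A late antibody response would probably not be seen, because the recall rule in 9.4.7 depends on serial titers that would no longer be collected.

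There is a secondary cost to the PK data. A subject who received the full assigned dose would contribute a shortened profile. Protocol 10.1 offers replacement only for subjects who were not dosed.

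**Working it through.** The plan states no figure on this point, so there is none to reproduce. The checks are what is lost, how much drug remains, and what happens to the AUC.

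**Inputs from the documents.** Half-life 10.5 days and subcutaneous (SC) peak at 3 days (Protocol 3.2). SC visits after Day 2 on Days 4, 8, 11, 15, 22, 29, 43, 57, 71 and 85, which is 10 visits, each with one PK sample; the IV arm has 9, without Day 11 (Schedule of Activities). Post-dose ADA samples on Days 15, 29 and 85, plus follow-up (9.4.7). Pregnancy tests on Days 29, 57 and 85, plus follow-up/ED. AUC(0-∞) is flagged above 20% extrapolation (SAP 9.3.1). Eighteen subjects per arm and a stated precision of 28% on the log scale (Protocol 5.1 and 10.1).

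**Assumptions.** The earlier half-life applies here. For the SC AUC only, a one-compartment model with first-order absorption. The documents give no rate of inadvertent enrollment; 0% to 3% is assumed.

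**Scheduled visits lost.** After ED at Day 8, Days 11, 15, 22, 29, 43, 57, 71 and 85 remain, so 8 are lost (7 for IV). After Day 15, 6 are lost. After Day 29, 4 are lost. The ED sample stands in for the follow-up sample in each case. ED at Day 8 also loses up to 3 pregnancy tests.

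**Drug remaining** = 2^(−t/10.5), with t = study day − 1. For t = 7, 14 and 28 this is 63.0%, 39.7% and 15.7%. It ignores SC absorption, so early SC values are approximate. Five half-lives: 5 × 10.5 = 52.5 days. By Day 57 about 2.5% remains, and by Day 85 about 0.4%.

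**Share of SC AUC(0-∞) extrapolated.** ke = ln 2/10.5 = 0.0660 per day. Solving ln(ka/ke)/(ka − ke) = 3 days gives ka = 0.958 per day. The fraction observed by time t is F(t) = 1 − (ka·e^(−ke·t) − ke·e^(−ka·t))/(ka − ke), and the extrapolated share is 1 − F(t). F = 0.323, 0.574, 0.731 and 0.831 at t = 7, 14, 21 and 28, and 0.996 at t = 84.

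**Effect of one truncated AUC(0-t_last) on the geometric mean of an arm of 18** = (F(t)/0.996)^(1/18) − 1. At Day 8: (0.323/0.996)^(1/18) − 1 = −6.1%.

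| ED at | SC visits (and PK samples) lost | ADA samples lost | Drug remaining | AUC(0-∞) extrapolated | Shift in arm geometric mean |
|---|---|---|---|---|---|
| Day 8 | 8 | 3 | 63% | 68% | −6.1% |
| Day 15 | 6 | 2 | 40% | 43% | −3.0% |
| Day 22 | 5 | 2 | 25% | 27% | −1.7% |
| Day 29 | 4 | 1 | 16% | 17% | −1.0% |

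ED at any visit up to Day 22 would exceed the 20% flag. If the peak is taken anywhere from 2 to 7 days, extrapolation is 26% to 33% at Day 22 and 16% to 21% at Day 29, so only Day 29 is borderline. The largest shift, −6.1%, is ln(0.939) = −0.063 on the log scale, against a stated half-length of 0.28.

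**Number affected.** 72 × 0.01 = 0.7 and 72 × 0.03 = 2.2, so 0 to 2.2 subjects.

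**The case against.** The strongest reply is that the protocol does not abandon these subjects and that the case is rare. Much of this stands.

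- The ED visit collects vital signs, ECG, laboratory tests, adverse event review, one PK sample and one ADA sample. Protocol 9.2 keeps serious, medically important or related events under follow-up. Protocol 9.2.1 requires notice of a related SAE learned of later and reporting of any pregnancy. Contraception is required for at least 3 months after dosing (6.1). Protocol 9.4.7 recalls subjects with non-decreasing titers above 1:1000. The release in 9.2.1 is permissive and does not forbid contact. All of this is real cover, but none of it actively looks for new events, and a single early ADA sample can miss a later response.
- A reader might infer that discontinuation has no benefit at all. It does end research procedures and blood draws in someone who did not qualify. Which default is better is partly a sponsor's choice.
- A reader might take a subject later found to meet the tuberculosis exclusion as the telling example. The documents do not support that: the tuberculosis test is done at screening only, so staying on schedule would add general review but no tuberculosis-specific monitoring.
- A reader might see a conflict with Protocol 10.3. There is none. That section analyses whatever evaluable PK data dosed subjects have and does not require complete profiles. SAP 9.3.1 flags high extrapolation but does not automatically exclude it, and SAP 8 lets deviations bear on population assignment.
- The design has slack: 72 enrolled for 64 completers, two spare per arm, with completion counted through Day 29 (5.2). The assumed upper case of 2.2 subjects fits within the eight spare unless they cluster in one arm or other dropout is high.

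**Conclusion.** The point holds as a gap in subject follow-up. Nothing else in the documents overrides 8.1.1. After the single dose it replaces the remaining visits to Day 85 with one ED visit, while drug is still present for about the first 7 to 8 weeks. The loss is greatest when ineligibility is found early (eight SC visits and three ADA samples at Day 8) and fades after about Day 54.

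It should not be read as a threat to the primary comparison. One truncated profile moves an arm's geometric mean by about 1% to 6%, and few such subjects are likely. Nor does it mean that these subjects go without any safety cover.

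The visit and sample counts come straight from the schedule. The drug-remaining figures rest on the earlier study's half-life, the AUC figures on the assumed one-compartment model, and the number affected on an assumed rate that includes zero. The documents also give no basis for predicting when ineligibility would be found. This is a cheap improvement that the sponsor should make.

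**What to change.** Amend 8.1.1 so that mandatory discontinuation applies only to subjects identified before dosing. For a dosed subject, record the unmet criterion and the date it was found as a deviation, inform the subject and, with the subject's agreement, continue the safety, ADA and PK visits already scheduled. Withdrawal for safety, by the investigator or by the subject stays available under 8.2. This is not an eligibility waiver: Section 6 bars prospective approval of deviations, not follow-up after an inadvertent one.

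In the SAP, decide inclusion in the PK population case by case under Section 8. Add one sentence prespecifying the bioavailability ratios with and without any subject whose unmet criterion could alter PK, for example prior LY3074828 (criterion 12) or a recent biologic (criterion 31).

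The cost is two or three sentences in a protocol amendment and one in the SAP. No subjects are added, and there are no visits beyond those planned: at most 10 SC or 9 IV outpatient visits after Day 2, plus follow-up, per affected subject. The downside is that an ineligible subject goes on giving blood samples, so agreement to continue must be confirmed.
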